9.1 Analysis Sets

The analysis populations will consist of patients as defined in Table 5.

Table 5 Analysis Data Sets

Analysis Data Sets	Description
Safety Analysis Set	Patients enrolled in the study who received at least 1 dose of treatment.
PK Analysis Set	Patients in the Safety Set with at least 1 plasma sample with a quantifiable concentration of PCS12852.
Full Analysis Set	Patients who are randomized.

9.2 Statistical Analyses

9.2.1 General Considerations

Approximately 24 patients (approximately 8 patients in each of the three treatment groups) with moderate to severe gastroparesis who have documented delayed gastric emptying are planned to be randomized (1:1:1) in the study. The randomization to treatment groups will be stratified by type of gastroparesis (idiopathic, diabetic), enrolling at least 2 patients of each type of gastroparesis (idiopathic, diabetic) in each treatment group.

9.2.2 Primary Efficacy Analysis

The change in the gastric emptying rate AUC as measured by the GEBT, from baseline to Day 28 will be analyzed in the FAS using an analysis of covariance (ANCOVA) model with treatment group (three levels) as a factor and the baseline GEBT as a covariate. Each of the two primary comparisons (0.1 mg versus placebo, 0.5 mg versus placebo), will be conducted using a two-sided Dunnett's test at the overall alpha=0.05 significance level.

Other efficacy analyses:

Version 3.0 55 of 85 20 April 2022

All secondary endpoints will be conducted using the same approach as described for the primary analysis. Each treated group will be compared to placebo using Dunnett's test. All secondary analyses will be based on the use of two-sided tests at the alpha=0.05 overall level of significance, with no adjustment for multiplicity.

Subgroup analysis:

A subgroup analysis of idiopathic gastroparesis patients compared to diabetic gastroparesis patients will be done for all efficacy analysis endpoints.

Pharmacokinetic analysis:

Plasma concentrations will be used to estimate the pharmacokinetic parameters for PCS12852 on Day 1 and Day 28 using noncompartmental methods in WinNonlin®. The following parameters will be calculated as data permits:

- C_{max}: maximum observed plasma concentration
- T_{max} : time at which the maximum plasma concentration was observed
- t_{1/2}: (the apparent first-order terminal elimination half-life)
- AUC_{0-last}: the area under the plasma concentration versus time curve, from time 0 to the last measurable concentration
- AUC $_{\infty}$: the area under the plasma concentration vs. time curve from time 0 to infinity
- λ_z : apparent first order terminal elimination rate constant

A dose proportionality analysis will be conducted for log-transformed Cmax, AUC0-last, and $AUC\infty$ using the power model. In addition, the relationship between gastric emptying rate and drug exposure will be assessed, as data permit. Exposure-response for safety measures may also be explored.

In addition, a population PK model may be used to describe the PK of PCS12852, if appropriate based on the data collected. A previously developed population PK model describing the PK of PCS12852 in patients with functional constipation, using a two-compartment model with first order absorption, may be used to predict the PK in patients in this study.

Further details of all analyses will be described in the SAP.

Version 3.0 56 of 85 20 April 2022

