The change in the gastric emptying rate AUC from baseline to Day 28 will be analyzed in the FAS using an analysis of covariance (ANCOVA) model with treatment group (three levels) and types (IG, DG) as a factor and the baseline GEBT as a covariate. Each of the two primary comparisons (0.1 mg versus placebo, 0.5 mg versus placebo) will be conducted using a two-sided Dunnett's test at the overall alpha=0.05 significance level.

Other efficacy analyses:

All secondary endpoints will be analyzed using the same types of ANCOVA models as described for the primary analysis. Each treated group will be compared to placebo. All secondary analyses will be conducted with no adjustment for multiplicity.

Subgroup analysis:

A subgroup analysis of idiopathic gastroparesis patients compared to diabetic gastroparesis patients will be performed for all efficacy analysis endpoints.

Pharmacokinetic Assessment

Plasma concentrations will be used to estimate the pharmacokinetic parameters for PCS12852 on Day 1 and Day 28 using noncompartmental methods in WinNonlin[®]. The following parameters will be calculated as data permit:

- C_{max}: maximum observed plasma concentration
- T_{max}: time at which the maximum plasma concentration was observed
- $t_{1/2}$: (the apparent first-order terminal elimination half-life)

Version 3.0 14 of 85 20 April 2022

Name of Investigational Product: PCS12852

Name of Active Ingredient: PCS12852

- AUC_{0-last}: the area under the plasma concentration versus time curve, from time 0 to the last measurable concentration
- AUC $_{\infty}$: the area under the plasma concentration vs. time curve from time 0 to infinity
- λ_z : apparent first order terminal elimination rate constant

A dose proportionality analysis will be conducted for log-transformed C_{max} , AUC_{0-last} , and AUC_{∞} using the power model. In addition, the relationship between gastric emptying rate and drug exposure will be assessed, as data permit. Exposure-response for safety measures may also be explored. Details of these analysis will be provided in the Statistical Analysis Plan.

In addition, a population PK model may be used to describe the PK of PCS12852, if appropriate based on the data collected. A previously developed population PK model describing the PK of PCS12852 in patients with functional constipation, using a two-compartment model with first order absorption, may be used to predict the PK in patients in this study.

Safety Analyses:

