For diabetic patients with gastroparesis, improvement of glucose control has been shown to increase antral contractility, correct gastric dysrhythmias and accelerate gastric emptying although there have been no long-term studies confirming the beneficial effects of maintaining euglycemia on gastroparetic symptoms (Parkman, 2004).

Treatments are based on the symptom presentation and usually include antiemetic agents or prokinetic agents. Currently the only treatment approved in the United States (US) for gastroparesis is metoclopramide (Prescribing information for Reglan, ANI Pharmaceuticals, Inc., Baudette, MN 2017; Prescribing information for Gimoti, Evoke Pharma, 2021). The currently approved indication for metoclopramide oral or nasal spray is relief of symptoms in adults with acute and recurrent diabetic gastroparesis (DG), although this medication has a black-box warning limiting treatment to no more than 12 weeks because of the risk of related side effects

Version 3.0 20 of 85 20 April 2022

including tardive dyskinesia. The 5-HT₄ agonist, cisapride, was previously used for the treatment of gastroparesis but was removed from the US market in 2000 because of cardiovascular risks.

Gastroparesis is a disease that affects a large number of people and can significantly impact the quality of life for those patients. With the limitation on currently approved treatments for gastroparesis there still is a need for new, effective treatments for this disorder.

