2.2 Background

PCS12852 (formerly known as YH12852) was previously developed by Yuhan Corporation (Korea) for the treatment of gastrointestinal motility disorders including chronic constipation, constipation-predominant irritable bowel syndrome, functional dyspepsia and gastroparesis.

Version 3.0 22 of 85 20 April 2022

Recently the product was acquired by Processa Pharmaceuticals, Inc. (Processa) and is being further developed for the treatment of gastroparesis.

Although there have been advances in understanding the mechanisms and pathophysiology of gastroparesis, there are still significant gaps in knowledge, inconsistencies across studies, and potential differences between different etiological groups (for example, diabetic versus idiopathic). Currently, the only FDA approved treatment for gastroparesis is metoclopramide. However, it carries a black box warning, as it is generally not well-tolerated and chronic use (>12 weeks) may lead to extrapyramidal side effects and potential irreversible tardive dyskinesia. Based on the limitations in currently available products for the treatment of gastroparesis, there still remains an unmet need for new treatments for these patients.

In support of the clinical development program for PCS12852, *in vitro, ex vivo* and *in vivo* pharmacology, safety pharmacology, pharmacokinetic and toxicology studies have been conducted. PCS12852 has been shown to have a high binding affinity for the 5-HT₄ receptor with more than 200-fold selectivity over other 5-HT receptors, as well as for 80 targets including receptors, ion channels and transporters. PCS12852 also exhibits 3.4 times more potent agonistic activity than tegaserod to human 5-HT_{4A} receptors stably expressed in Chinese hamster ovaries (CHO). In studies of *ex vivo* contractile activity in guinea pig colon, PCS12852 was found to be 17 times more potent than 5-HT.

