6.3 Measures to Minimize Bias: Randomization and Blinding

Patients who have successfully completed Screening criteria (Visit 1 and Visit 2) will return for a Randomization visit (Visit 3) where the inclusion/exclusion criteria will be evaluated and patients who meet the criteria will be randomized in a 1:1:1 ratio into one of the three treatment groups, PCS12852 0.1mg, PCS12852 0.5mg or placebo via Interactive Response Technology (IRT). The planned sample size to be randomized is 24 patients. The randomization to treatment groups will be stratified by type (IG, DG), enrolling at least 2 patients of each type in each treatment group.

The list of treatment allocations will be kept in a secure location by the CRO until approval to unblind is provided for the final analysis. Access to the treatment allocations will be monitored by Regulatory Affairs/Quality Assurance; any access to the allocations prior to unblinding the study will be documented by Regulatory Affairs/Quality Assurance and included in the Clinical Study Report.

Table 4 Measures to Minimize Bias

Study using IRT	All patients will be centrally randomized using an Interactive Response Technology (IRT). Each patient will be assigned a unique number (randomization number) that encodes the patient's assignment to one of the 3 arms of the study, according to the randomization schedule using a validated computer program. Details of the procedure are described in the IRT Manual provided to all sites.
	Study treatment will be administered/dispensed at the study visits as summarized in the SoA (Table 1).
	Returned study treatment should not be re-dispensed to the patients.

Version 3.0 38 of 85 20 April 2022

Blind break (IRT)

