6.7.2 Permitted Treatments

Any medication or vaccine (including over-the-counter or prescription medicines, vitamins, and/or herbal supplements) that the patient is receiving at the time of enrollment or receives during the study must be recorded in the eCRF along with:

- indication
- dates of administration including start and end dates
- dosage information including dose and frequency

Diabetic gastroparesis patients enrolled in the study will likely consist mostly of patients receiving one or more prescription medications for blood-glucose control. Good clinical practice allows for frequent adjustment of medication by patients and their health care providers to minimize large fluctuations in glycemia, and this practice is encouraged in this study.

It should be remembered that certain diabetic drugs (see Section 6.7.1) delay gastric emptying and are prohibited during this study. Other therapy considered necessary for the patient's welfare

Version 3.0 41 of 85 20 April 2022

may be given at the discretion of the Investigator. If the permissibility of a specific medication/treatment is in question, please contact the Medical Monitor.

The Medical Monitor or designee should be contacted if there are any questions regarding concomitant or prior therapy.

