8.4 Pharmacokinetics

Blood samples will be collected for measurement of PCS12852 in plasma via a specific and sensitive validation bioanalytical method, at timepoints as specified in the SoA (Table 1). Clinical staff are encouraged to take the blood samples for PK analysis at the scheduled time point; however, deviations from the scheduled sample times are not considered protocol deviations. The actual date and time (24-hour clock time) of sample collections will be recorded in the source document and transcribed into the eCRF. Instructions for the collection and handling of biological samples will be provided in the Study Manual.

Samples will be used to evaluate the PK of PCS12852. Samples collected for analyses of PCS12852 plasma concentration may also be used to evaluate safety or efficacy aspects that address concerns arising during or after the study.

Genetic analyses will not be performed on these blood samples. Subject confidentiality will be maintained.

Any changes in the timing or addition of time points for any planned study assessments must be documented and approved by the relevant study team member and then archived in the Sponsor and site study files but will not constitute a protocol amendment. The IRB/IEC will be informed of any safety issues that require alteration of the safety monitoring scheme or amendment of the ICF.

Version 3.0 54 of 85 20 April 2022

9 Statistical Considerations

The statistical analysis plan (SAP) will be developed and finalized before database lock and will include a more technical and detailed description of the statistical analyses described in this section. This section is a summary of the planned statistical analyses of the most important endpoints including primary and key secondary endpoints.

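### The primary ANCOVA includes gastroparesis type (the randomization stratum) in the Synopsis but not in Section 9.2.2, and nothing says which model governs

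*Combined protocol and SAP*

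**What the plan says.** Two current parts of Version 3.0 specify the primary analysis of change in GEBT AUC to Day 28 in the full analysis set.

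- Synopsis (Section 1.1), Primary Efficacy Analyses: an ANCOVA "model with treatment group (three levels) and types (IG, DG) as a factor and the baseline GEBT as a covariate".
- Section 9.2.2: an "analysis of covariance (ANCOVA) model with treatment group (three levels) as a factor and the baseline GEBT as a covariate".

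Both then apply a two-sided Dunnett test to the two dose-placebo comparisons at overall alpha 0.05. Section 6.3 says: "The randomization to treatment groups will be stratified by type (IG, DG), enrolling at least 2 patients of each type in each treatment group". Section 9.2.1 repeats the stratification.

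Each part tells the secondary endpoints to follow its own primary analysis. Section 9.2.2 also names Dunnett's test for them and then says there is no adjustment for multiplicity. The Synopsis says only the latter.

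Section 9 opens with: "This section is a summary of the planned statistical analyses". It leaves technical detail to an SAP to be finalized before database lock. No SAP text settling the model is in the document supplied, and no rule ranks the Synopsis against the body.

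**The concern.** The protocol gives two different primary models, and the difference is the factor used to stratify the randomization. An analysis normally carries its stratification factor. Without it, any difference in mean change between IG and DG patients stays in the residual, although the design has already balanced it across arms.

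The protocol itself gives reasons to think type could matter. Section 2.2 mentions "potential differences between different etiological groups (for example, diabetic versus idiopathic". Section 2 says that in diabetic patients "improvement of glucose control has been shown to increase antral contractility, correct gastric dysrhythmias and accelerate gastric emptying". Section 6.7.2 describes adjusting glucose medication "to minimize large fluctuations in glycemia, and this practice is encouraged in this study".

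With 8 patients per arm, the primary p-value and interval depend on which page is followed. If this is still open at unblinding, the sponsor would be choosing between two documented primary analyses with the results in view.

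**Working it through.** **1. The two texts side by side**

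| | Synopsis | Section 9.2.2 |
|---|---|---|
| Endpoint, set | GEBT AUC change, FAS | same |
| Factors | treatment, type | treatment |
| Covariate | baseline GEBT | same |
| Primary test | Dunnett, overall 0.05 | same |
| Error df (24 patients) | 24 − 5 = 19 | 24 − 4 = 20 |
| Dunnett critical value | 2.388 | 2.379 |

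**2. The plan's own power figure.** Section 9.3 gives 8 per arm, SD 15, difference 25, two-sided alpha 0.025 and 80% power. The noncentrality is 25 / (15 × √(2/8)) = 3.33. A two-sample t-test on 14 df gives 78.4%. Dunnett's test on 20 or 19 df gives 82.2% or 81.9%. The stated 80% reproduces, and the sample size does not depend on which model is used.

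**3. Why omission is conservative.** Let *g* be the IG/DG gap in mean change, with 4 patients of each type per arm. The arms are balanced for type, so *g* does not affect the treatment contrast. Its sum of squares, 24 × (g/2)² = 6g², goes into the residual. The residual mean square rises by roughly 6g²/20. For g = 15 and within-type SD 15 it becomes 225 + 67.5 = 292.5, so standard errors are overstated by √(292.5/225) = 1.14. Simulated interval half-widths agree: 20.53 without type and 18.18 with it, a ratio of 1.13.

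**4. Size.** Both models were fitted to the same simulated trials, with 24 patients, a difference of 25 for each dose, Dunnett critical values and baseline assumed not prognostic. The gaps are assumptions. Section 9.3 does not mention strata, so SD 15 is read two ways:

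- **A**, total SD 15. The within-type SD is √(225 − g²/4).
- **B**, within-type SD 15. The total SD is √(225 + g²/4), that is 15.5, 16.8 and 18.8 for gaps of 7.5, 15 and 22.5.

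Results for a 4/4 split per arm, good to within about a point for power and disagreement:

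| Reading | Gap | Power without type | Power with type | Familywise error without type | Models disagree on a given dose |
|---|---|---|---|---|---|
| – | 0 | 80.1% | 79.7% | 5.0% | 2% |
| A | 7.5 | 80% | 82% | 4.2% | 3% |
| A | 15 | 82% | 90% | 2.1% | 9% |
| A | 22.5 | 85% | 99% | 0.3% | 14% |
| B | 7.5 | 78% | 80% | 4.2% | 3% |
| B | 15 | 70% | 80% | 2.6% | 10% |
| B | 22.5 | 59% | 80% | 1.2% | 21% |

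With type in the model, familywise error stays at 5.0%. With a 2/6 split (the protocol's minimum of 2 of a type per arm), power without against with type at gaps 7.5, 15 and 22.5 is:

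- A: 80/82%, 81/88%, 83/96%
- B: 78/80%, 73/80%, 64/80%

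**5. Choosing after the fact.** Reporting whichever model rejects raises familywise error to at most 5.4%.

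**6. Secondary wording.** At 20 df the critical |t| is 2.38 with Dunnett and 2.09 unadjusted. Error over the two doses within one endpoint is 5.0% or 8.9% accordingly.

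**The case against.** The strongest reply is that little is at risk. An SAP is promised before database lock, and Section 6.3 keeps the allocations secure until unblinding is approved. If that SAP names one model, there is no post hoc choice. Neither model inflates error, and even picking the favourable one reaches only 5.4%. The large losses need large gaps: 15 units is 60% of the planned effect of 25, and 22.5 is 90%. No document gives any gap. At 7.5 the loss is about 2 points. Section 9.3 describes 15 simply as the SD of the change, which favours reading A, and there the Section 9.2.2 model never falls below the planned 80%. The passages on diabetic and idiopathic differences do not speak of GEBT change over 28 days, so a prognostic effect of type is an inference.

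All of this limits the size, and most of it stands. It does not remove the conflict. Deferring detail to an SAP does not tell its author which of two protocol models to detail. The separate IG/DG subgroup analysis does not replace a type term in the primary model.

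On the secondary endpoints, Dunnett across the two doses with nothing across endpoints is a coherent reading of Section 9.2.2. That point is an ambiguity, not a contradiction.

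**Conclusion.** The concern holds. The primary model is specified in two incompatible ways, the difference is the randomization stratum, and the secondary endpoints inherit the conflict.

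The consequence is lost precision and an open choice of model, not false positives. If type is not prognostic, the choice barely matters: about 0.5 points of power, and different verdicts on a given dose in 2% of trials. At an assumed 15-unit gap (4/4 split), the Section 9.2.2 model gives up about 8 to 10 points of power. Under the total-SD reading this is a loss against the better model, not a shortfall against the planned 80%. Under the within-type reading it is a shortfall.

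These figures rest on assumed gaps, a baseline that does not predict change, and equal effects for both doses. The conflict should be fixed, but it does not threaten validity.

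**What to change.** In Section 9.2.2, the Synopsis and the SAP, state one primary model before unblinding:

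- change in GEBT AUC = treatment (three levels) + type (IG/DG) + baseline GEBT AUC.

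Use the same form for each secondary endpoint with its own baseline, which for the ANMS GCSI-DD is the Day −7 to Day −1 score. In both the Synopsis and Section 9.2.2, say that Dunnett's test covers the two dose-placebo comparisons within each secondary endpoint. Keep the statement of no multiplicity adjustment, but limit it to comparisons across endpoints and time points.

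The cost is a few sentences and one error degree of freedom (20 to 19). Conduct and sample size do not change.

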9.3 Sample Size Determination

Based on the results of a prior study (Study 102), estimates of the standard deviation (SD) of the AUC change from baseline range from 10 to 35. Assuming a true SD of 15 and based on a two-sided test at the alpha=0.025 level of significance, a sample size of 8 patients per arm (24 total patients) will provide 80% power to detect a between-group mean difference of 25.

Version 3.0 59 of 85 20 April 2022

10 Supporting Documentation and Operational Considerations

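### The primary Dunnett test is named without a step-down rule; adding one keeps the 5% family-wise error and gains about 4 points of power per dose at the planning values

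*Combined protocol and SAP*

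**What the plan says.** Two places in the protocol define the primary test, and they agree on the procedure.

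- Section 9.2.2: the sentence begins "Each of the two primary comparisons (0.1 mg versus placebo, 0.5 mg versus placebo), will be conducted using a two-sided" and goes on to name Dunnett's test. The level is set "at the overall alpha=0.05 significance level".
- Section 1.1 (Synopsis): the sentence begins "Each of the two primary comparisons (0.1 mg versus placebo, 0.5 mg versus placebo) will be conducted using a two-sided" and likewise names Dunnett's test, with the same overall level.

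The models differ slightly. Section 9.2.2 has "treatment group (three levels) as a factor and the baseline GEBT as a covariate". The Synopsis has "treatment group (three levels) and types (IG, DG) as a factor", again with baseline as covariate.

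Section 9.3 sizes each comparison with a "two-sided test at the alpha=0.025 level of significance", 8 patients per arm, a difference of 25 and 80% power. It states "Assuming a true SD of 15", against Study 102 estimates of the SD of the AUC "change from baseline range from 10 to 35".

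No step-down, closed or ordered procedure is named anywhere, and no confidence intervals are planned for the primary comparisons. Section 9.2.2 leaves further analysis detail to the SAP, but the documents contain no SAP text on this point.

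**The concern.** In the single-step Dunnett test, both doses must exceed the two-comparison critical value. Once the dose with the larger absolute t has exceeded it, closed testing allows the other dose to be tested at the ordinary two-sided 5% t value, with family-wise error still at 5%. The plan as worded does not use this.

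The study is titled a dose response study, and its primary efficacy objective concerns the effect of different doses, so the result on each dose matters. With 8 patients per arm, a second dose could be called non-significant because of an adjustment that is no longer needed to protect the 5% level.

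**Working it through.** **Inputs.** From Section 9.3: 8 per arm, SD 15, difference 25, SD range 10 to 35. From Section 9.2.2: two-sided test, overall alpha 0.05. Error degrees of freedom with 24 patients: 24 − 3 arms − 1 covariate = 20 (Section 9.2.2 model), or 19 with gastroparesis type added (Synopsis model). With 1:1:1 allocation, the two comparisons share the placebo arm and have correlation 0.5. SD 15 is taken as the residual SD; any gain in precision from the baseline covariate is ignored.

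**The plan's own figure.** Standard error of a difference = 15 × √(2/8) = 7.5. Noncentrality = 25/7.5 = 3.333. At two-sided alpha 0.025, the noncentral t gives 78.4% power with 14 df (two arms only) and 81.3% with 21 df (SD pooled over three arms). The stated 80% is reproduced.

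**Critical values at 20 df.** Single-step Dunnett for two comparisons: 2.379, a per-comparison two-sided level of 0.0275. Ordinary two-sided 5% t value, used at the second step: 2.086.

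**Why step-down loses no rejections.** Its first step is the same comparison with 2.379. Its second step is reached only after a rejection and uses the lower value. Every extra rejection therefore occurs in a trial that already has one significant dose. The chance of at least one significant dose cannot change, and the gain in the chance of both equals the sum of the two per-dose gains.

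**Power at the planning values** (2,000,000 simulated trials, 20 df, SD 15, difference 25 at both doses):

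| | Single-step | Step-down | Gain (points) |
|---|---|---|---|
| Power per dose | 82.2% | 86.4% | 4.2 |
| Both doses significant | 72.4% | 80.8% | 8.4 |
| At least one significant | 91.9% | 91.9% | 0 |

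Check: 4.2 + 4.2 = 8.4. With the Synopsis model (19 df, critical values 2.388 and 2.093), per-dose power goes from 81.9% to 86.1% and both doses from 72.1% to 80.5%.

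**Family-wise error.** 5.0% with both doses inactive, and 5.0% with one dose inactive and the other certain to be rejected.

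**Sensitivity to the SD**, with 25 at both doses (20 df):

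| SD | Single-step, per dose | Step-down, per dose | Gain (points) |
|---|---|---|---|
| 10 | 99.3% | 99.7% | 0.4 |
| 15 | 82.2% | 86.4% | 4.2 |
| 20 | 55.6% | 60.7% | 5.1 |
| 25 | 37.2% | 41.3% | 4.1 |
| 35 | 19.4% | 21.7% | 2.2 |

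**Sensitivity to unequal effects.** These effects are assumptions, since the documents give none by dose. SD is 15 and 0.5 mg is set at 25:

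- 0.1 mg at 20: its power rises from 61.7% to 69.7%, a gain of 8.0 points.
- 0.1 mg at 15: from 37.2% to 46.5%, a gain of 9.3 points.
- 0.1 mg inactive: power for 0.5 mg rises by 0.1 point. The chance of a false rejection for 0.1 mg rises from 2.7% to 4.5%, still within 5%.

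The largest gain found for a dose is about 10.5 points, and it needs the other dose to be virtually certain of rejection (15 at one dose, 50 at the other).

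**The case against.** The strongest reply is that nothing here is wrong. The planned test controls family-wise error, and its power per dose of about 82% meets the 80% target. No passage contradicts another on the procedure, and no success rule requires both doses to be significant. The chance of finding at least one active dose is the same either way. All of this stands, and it limits the point to a cheap improvement.

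The protocol also does not say single-step. That is the usual reading of an unqualified Dunnett's test, but the deferral to the SAP leaves the step-down form open. This stands too, and is a further reason to name the variant.

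A reader might infer that the trial gives up 4 to 10 points of power on a dose for nothing. The documents do not support that, for three reasons.

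- At the planning values the gain is at the bottom of that range, and it falls to 0.4 or 2.2 points at the ends of the SD range. The 8 to 9 point gains rest on assumed unequal effects.
- A reader might also infer that 0.1 mg bears most of the loss. That presumes 0.5 mg has the larger effect. In Section 2.1, the Study 102 breath-test results for the immediate-release formulation cover only 0.05 mg and 0.1 mg; doses of 0.5 mg and above used the delayed-release formulation.
- The single-step test has matching simultaneous intervals, and step-down has none as simple. An extra rejection arises when the second absolute t lies between 2.086 and 2.379. With a standard error of 7.5, that is an estimated difference between 2.086 × 7.5 = 15.6 and 2.379 × 7.5 = 17.8. The single-step interval then includes zero. This plan names no such intervals, so it makes no use of that advantage, but the conflict must be handled if intervals are shown.

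**Conclusion.** The point holds as an efficiency improvement. On the ordinary reading, the plan uses a valid single-step test where a step-down test at the same 5% family-wise error would reject everything it rejects and sometimes one dose more. At SD 15 with 25 at both doses, the gain is about 4 points per dose (82% to 86%) and about 8 points for both doses (72% to 81%). The chance of at least one significant dose is unchanged at about 92%.

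These figures assume that both doses are active, that the residual SD equals the planned SD, and that all 24 patients contribute. The conclusion is the same under either ANCOVA model. It does not show that the trial is underpowered against its stated target or that the planned test is incorrect.

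**What to change.** In Section 9.2.2, the Synopsis and the SAP, before unblinding, write: *two-sided step-down Dunnett test at overall alpha 0.05: the larger absolute t is compared with the two-comparison Dunnett critical value; if significant, the other dose is tested at the two-sided 0.05 t value.*

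Add two clarifications.

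- State whether the secondary endpoints follow the same rule. Section 9.2.2 applies the primary approach and Dunnett's test to them while also saying that multiplicity is not adjusted for; the Synopsis does not name Dunnett's test for them.
- If single-step Dunnett intervals are reported, state that the test decides significance, because a dose rejected only at the second step will have an interval that includes zero.

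The cost is a few sentences and a standard software option. Sample size, visits and conduct do not change. The one real downside is that mismatch between test and interval for a dose rejected at the second step.
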